### 8.3 Diary Review

The diary should be reviewed at every visit by the investigator, or suitably qualified designee, and the subject. Any subject-recorded comment captured in the diary considered an AE will be assessed and reported as described in Section 10.

Any additional comments relating to medications/treatments captured in the diary will be reviewed by the investigator, or medically qualified designee, with the subject and recorded in the eCRF as appropriate. Additional and missed product applications will be considered deviations from the protocol and will be recorded on the Deviations Log and captured as a deviation in the eCRF.

Property of GSK Consumer Healthcare - Confidential

May not be used, divulged, published or otherwise disclosed without the consent of  
 GSKCH

CCI

Clinical Protocol Template v7.0

Page 55 of 100

## 8.4 Study Conclusion

The Study Conclusion page of the eCRF will be completed for all subjects whether they completed all study procedures or were discontinued early. If the subject was discontinued at any point during the study, the primary reason for withdrawal should be recorded on the Study Conclusion page.

If a subject has any clinically significant, study-related abnormalities or AEs at the end of the study, the GSK CH medical monitor (or designated representative) should be notified; the subject may be asked to remain at the clinical site or be asked to return for a follow-up visit to ensure any issue is resolved or deemed not clinically significant.

## 8.5 Follow-up Visit/Phone Call

The study site may contact a subject to follow up an AE post-study completion/withdrawal and, in some circumstances, request they return to the site for additional follow-up visits (final safety assessments). If needed, additional clinical examinations may be carried out at such visits.

# 9 STUDY ASSESSMENTS

Every effort should be made to ensure that protocol-required assessments are completed as described. However, it is anticipated there may be circumstances, outside the control of the investigator, that may make it unfeasible to complete an assessment. In these cases, the investigator must take all steps necessary to ensure the safety and well-being of the subject. When a protocol-required assessment cannot be performed, the investigator (or designee) will document the reason for the missed assessment as a protocol deviation and any corrective and preventative actions they have taken to ensure the required procedures were adhered to as soon as possible. The Sponsor must be informed of any missed assessments in a timely manner.

To ensure the clinical examiner/staff involved in safety/product performance assessments remain blind to product received throughout the study, site staff involved in the dispensing of study product and the supervision of on-site product usage will work in a separate area; the examiner will not be permitted in any area where study product is stored, dispensed or in use; study subjects will be instructed not to remove study product from the opaque bags

Property of GSK Consumer Healthcare - Confidential

May not be used, divulged, published or otherwise disclosed without the consent of  
GSKCH

CCI

Clinical Protocol Template v7.0

Page 56 of 100

provided, outside of the dispensing room, while at the study site; dispensing staff will not be involved in any safety/product performance assessment procedures during the study.

## 9.1 Screening Assessments

Screening assessments will be performed by appropriately trained staff/clinical examiners at the times, and in the order, defined in the [Study Procedures](#) section of this protocol (Section 8). Eligible tooth assessments will be accomplished by oral examination and will evaluate dentition exclusions, EAR, MGI, tooth mobility and sensitivity to tactile and evaporative (air) stimuli. Eligibility assessments will be carried out by the investigator, or qualified designee, against the inclusion/exclusion criteria. Ineligible subjects will not be re-screened.

### 9.1.1 Erosion, Abrasion and Recession (EAR)

The facial surfaces of all incisor, canine and pre-molar teeth that do not present any of the general dentition exclusion criteria, or specific dentition exclusion criteria for eligible teeth, will be examined for signs of cervical EAR (Addy, 2002).

### 9.1.2 Modified Gingival Index (MGI)

The MGI is a non-invasive, visual assessment of gingival health (Lobene, 1986). MGI will be assessed for incisor, canine and pre-molar teeth exhibiting none of the dentition exclusions and facial/cervical EAR. MGI will be scored for the facial gingiva only, adjacent to the test area (exposed dentine). Eligible teeth will have a MGI score of zero.

Score	Description
0	Absence of inflammation
1	Mild inflammation; slight change in colour, little change in colour; little change in texture of any portion of the marginal or papillary gingival unit.
2	Mild inflammation; criteria as above but involving the entire marginal or papillary gingival unit.
3	Moderate inflammation; glazing, redness, edema, and/or hypertrophy of the marginal or papillary gingival unit.
4	Severe inflammation; marked redness, edema and/or hypertrophy of the marginal or papillary gingival unit, spontaneous bleeding, congestion, or ulceration.

Property of GSK Consumer Healthcare - Confidential

May not be used, divulged, published or otherwise disclosed without the consent of  
 GSKCH

CCI ██████████ Clinical Protocol Template v7.0

Page 57 of 100

### 9.1.3 Tooth Mobility Assessment

Clinical mobility will be assessed for incisor, canine and pre-molar teeth exhibiting none of the dentition exclusions, facial/cervical EAR and MGI = 0, using a modification of the Miller Index (Laster et al., 1975). Eligible teeth will have clinical mobility = 0.

Degree	Description
0	No movement or mobility of the crown of the tooth < 0.2 millimeter (mm) in a horizontal direction.
1	Mobility of the crown of the tooth 0.2 – 1 mm in a horizontal direction
2	Mobility of the crown of the tooth exceeding 1 mm in a horizontal direction
3	Mobility of the crown of the tooth in a vertical direction as well

### 9.1.4 Qualifying Tactile Sensitivity (Visit 1)

The tactile sensitivity of incisor, canine and pre-molar teeth exhibiting none of the dentition exclusions, and meeting the EAR, MGI and clinical mobility criteria, will be assessed using a constant pressure probe (Yeaple probe (Polson et al., 1980). The probe tip will be placed perpendicular to the facial surface of the tooth and drawn slowly across the exposed dentine to ensure application of the stimulus across the potentially 'sensitive' area. After each application, the subject will be asked to indicate whether they experienced any sensitivity or discomfort (yes/no response only). The subject may respond "yes" if they feel pressure as the probe is applied to their tooth. The examiner will remind them they should only respond 'yes' if they feel sensitivity or discomfort. The gram setting which elicits the two consecutive 'yes' responses will be recorded as the tactile threshold (g). At Screening, the upper force setting will be 20 g.

**For a tooth to qualify at Screening, it must have a tactile threshold  $\leq$  20 g. If no sensitivity is found at the upper setting, the tactile threshold will be recorded as  $>$  20 g and the tooth will be disqualified from further testing.**

If a subject fails to give a definite answer, the examiner will re-prompt them to provide response. If uncertainty continues, this will be indicated on the clinical assessment score sheet/in the eCRF. If the subject continues to be unsure, or the examiner is unsure of the reliability of their response, the examiner may opt to re-probe at the same force setting

Property of GSK Consumer Healthcare - Confidential

May not be used, divulged, published or otherwise disclosed without the consent of  
 GSKCH

CCI

Clinical Protocol Template v7.0

Page 58 of 100

(indicated to the assistant by a non-verbal signal, i.e. a hand gesture), or move to the next force setting (10 g increase).

The examiner will generally make the pressure setting adjustments (may be carried out by an assistant/scribe); the scribe will record the micro-amperage setting and the subject's responses in a source document.

### **Calibration of the Yeaple Probe:**

The Yeaple probe will be calibrated by an appropriately trained member of the study staff (typically the clinical examiner or their assistant/scribe) before use on each day subjects are assessed. The microamp settings may vary from day to day (partly due to battery power consumption), but the difference should not be significant. Thus, previous probe settings can serve as a guide. Calibration should start at the lowest microamp setting and then increase. Either calibration method described below is acceptable.

- **Method 1 ('Water Cup'):** The Yeaple probe is fixed to a clamp attached to a ring stand so that the probe tip is vertical. A small paper cup attached with cotton thread is balanced over the end of the Yeaple probe, without the probe tripping.

The probe dial is set to the microamp setting and water is fed into the paper cup using a dropper until the probe trips. The gram setting is recorded and the Yeaple probe reset to the next microamp value. The procedure is repeated until data has been collected to more than 80 g.

- **Method 2:** The Yeaple probe is fixed to a clamp attached to a ring stand so that the top is perpendicular to the pan of an ohaus dial-o-gram® balance or equivalent. The probe tip is positioned to just touch the pan when the balance is set at zero grams. The probe dial is set to the microamp setting and the gram setting is increased on the balance until the probe trips. The gram setting is recorded and the Yeaple probe reset to the next microamp value.

The data are plotted, and the points connected with line segments in order to interpolate the micro-amp values equivalent to 10, 20, 30, 40, 50, 60, 70 and 80 g. This calibration should be repeated three times, and the average of the three used for the day's settings.

The settings will be recorded on the Yeaple probe calibration record (along the probe's serial number) which will serve as the force setting guide for that day's examinations.

Property of GSK Consumer Healthcare - Confidential

May not be used, divulged, published or otherwise disclosed without the consent of  
 GSKCH

CCI

Clinical Protocol Template v7.0

Page 59 of 100

### **9.1.5 Qualifying Evaporative Air Sensitivity (Visit 1)**

Evaporative (air) sensitivity will be assessed on the facial surfaces of incisor, canine and pre-molar teeth exhibiting none of the dentition exclusions, and meeting the EAR, MGI, clinical mobility criteria, with a tactile threshold ( $\leq 20$  g) criteria; assessment will commence a minimum of 5 minutes after the tactile assessments have been completed. The assessment will be made by directing a one second application of air from a standard dental syringe held perpendicular to the tooth surface, approximately 1-2 mm coronal to the gingival margin, and from a distance of approximately 1 centimeter. The examiner will take appropriate measures to isolate the tooth surface to prevent stimulation of adjacent teeth or surrounding soft tissue.

Subject response to the stimulus will be evaluated using the Schiff sensitivity scale (Schiff et al., 1994). This is an examiner-based index, scored immediately following administration of the evaporative (air) stimulus. This scale focuses on a combination of specific, observable, physical, behavioural and verbal responses from the subject, which may facilitate discrimination.

**For a tooth to qualify at screening, it must have a Schiff sensitivity score  $\geq 2$ . If Schiff sensitivity score = 0 or 1, the tooth will be disqualified from further testing.**

## **9.2 Product Performance Assessments**

The following product performance assessments will be performed by appropriately trained staff/clinical examiners (who are blind to product received), at the times and in the order defined in the [Study Procedures](#) section of this protocol ([Section 8](#)).

### **9.2.1 Dentine Hypersensitivity Experience Questionnaire (DHEQ)**

A 'short form' DHEQ (Appendix I: Example DHEQ-15) will be completed by each study subject at Baseline (Visit 2), Day 3 (Visit 3), Week 2 (Visit 4), Week 4 (Visit 5) and Week 8 (Visit 6), prior to the OST examination and clinical assessments.

The DHEQ is divided into two sections - Section 1 asks questions about 'your sensitive teeth and the impact it has on your everyday life'; Section 2 asks questions about 'the ways in which the sensations in your teeth affect you in your daily life' grouped into the following domains.

Property of GSK Consumer Healthcare - Confidential

May not be used, divulged, published or otherwise disclosed without the consent of  
 GSKCH

CCI

Clinical Protocol Template v7.0

Page 60 of 100

- Restrictions (Section 2, Q1-3)
- Adaptation (Section 2, Q4-6)
- Social Impact (Section 2, Q7-9)
- Emotional Impact (Section 2, Q10-12)
- Identity (Section 2, Q13-15)

[figure not shown]
At Baseline, all questions will be answered - Section 1 (Q1-9) and Section 2 (Q1-15)

At Day 3, Week 2, Week 4 and Week 8, Section 1 (Q7-9 only) and Section 2 (Q1-15) will be answered.

### 9.2.2 Self-Perceived Sensitivity Discomfort Assessment

The 11-item Numeric Rating Scale (NRS) is a segmented numeric version of the visual analog scale (VAS) in which a respondent selects the number (0–10) that best reflects the intensity of the discomfort caused by their sensitivity (Hawker et al., 2011, Rocha et al., 2020). Similar to the VAS, the NRS is anchored by terms describing discomfort extremes and ranges from 0 = no discomfort to 10 = worst discomfort imaginable.

An NRS (example below) will be completed by each study subject at Baseline (Visit 2), Day 3 (Visit 3), Week 2 (Visit 4), Week 4 (Visit 5) and Week 8 (Visit 6), after the DHEQ but prior to the OST examination and clinical assessments.

Property of GSK Consumer Healthcare - Confidential  
 May not be used, divulged, published or otherwise disclosed without the consent of  
 GSKCH

### 9.2.3 Tactile Sensitivity Assessment

**Visit 2:** The tactile sensitivity of all qualifying teeth from Screening (i.e., teeth that exhibited none of the dentition exclusions, met the EAR, MGI, clinical mobility and qualifying tactile threshold/Schiff sensitivity score criteria) will be assessed at Baseline.

**Visits 3-6:** The tactile sensitivity of the two ‘test teeth’ selected by the clinical examiner at Baseline will be assessed for randomised subjects. The tactile stimulus will be administered and subject response recorded, as described in Section 9.1.4. The gram setting which elicits the two consecutive ‘yes’ responses will be recorded as the tactile threshold (g).

At Baseline (Visit 2), the upper force setting will be 20 g; at all subsequent visits (Visits 3-6), the upper force setting will be 80 g. If no sensitivity is found at the upper setting, the tactile threshold will be recorded as > 20 g at Baseline, and as > 80 g on Day 3, Week 2, 4 and 8.

### 9.2.4 Evaporative (Air) Sensitivity Assessment

**Visit 2:** The evaporative (air) sensitivity of all qualifying teeth from Screening will be assessed at Baseline.

**Visits 3-6:** The evaporative (air) sensitivity of the two ‘test teeth’ selected at Baseline will be assessed first for all randomised subjects; this will be followed by the assessment of evaporative (air) sensitivity for all remaining eligible teeth identified at Screening.

The evaporative (air) stimulus will be administered, and subject response recorded, as described in Section 9.1.5. On every occasion, the evaporative (air) assessment of the two test teeth will begin a minimum of 5 minutes after the last tactile assessment has been completed (to allow tooth recovery time).

Score	Description
0	Subject does not respond to stimulus
1	Subject responds to stimulus but does not request discontinuation of stimulus
2	Subject responds to stimulus and requests discontinuation of, or moves from stimulus
3	Subject responds to stimulus, considers it uncomfortable and requests discontinuation of stimulus

Property of GSK Consumer Healthcare - Confidential

May not be used, divulged, published or otherwise disclosed without the consent of  
 GSKCH

CCI

Clinical Protocol Template v7.0

Page 62 of 100

### **9.2.5 Selection of Test Teeth**

On completion of the Baseline clinical assessments, the clinical examiner will select two 'test teeth' for each eligible subject, to be evaluated first at all subsequent visits. The test teeth will exhibit none of the dentition exclusions and meet all the inclusion criteria for eligible teeth (including Screening and Baseline tactile threshold  $\leq 20$  g; Screening and Baseline Schiff sensitivity score  $\geq 2$ ). Test teeth should not be adjacent to each other and preferably in different quadrants.

## **9.3 Safety and Other Assessments**

The following safety assessments will be performed by appropriately trained staff/clinical examiners, at the times and in the order defined in the [Study Procedures](#) section of this protocol ([Section 8](#)).

### **9.3.1 Oral Soft Tissue (OST) Examination**

The OST examination will be accomplished by direct observation and palpation, using retraction aids as appropriate, and will include examination of the labial mucosa (including lips), buccal mucosa, and mucogingival folds, gingival mucosa, hard palate, soft palate, tonsillar area, pharyngeal area, tongue, sublingual area, submandibular area and salivary glands. The results of the examination will be recorded in the eCRF as either normal or abnormal with details of any abnormalities. Any abnormality or worsening of a pre-existing condition observed by the clinical examiner or reported by the subject from the OST examination carried out at Screening will be recorded as an AE.

### **9.3.2 Oral Hard Tissue (OHT) Examination**

The OHT examination will be accomplished by direct observation, using retraction aids as appropriate and will identify any grossly carious lesions or signs of erosive wear, enamel irregularities, tooth fracture, gross decay, decalcification and faulty restorations.

The presence of any implants, fixed or removable dentures, fixed or removable orthodontic braces/bands, fixed orthodontic retainers, full crowns or veneers will be recorded. Observations will be listed as either absent or present, and conditions noted as present will be described in the eCRF. Any change observed by the clinical examiner or reported by the subject from the OHT examination carried out at Screening will be recorded as an AE.

Property of GSK Consumer Healthcare - Confidential

May not be used, divulged, published or otherwise disclosed without the consent of  
 GSKCH

CCI

Clinical Protocol Template v7.0

Page 63 of 100

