## **10            ADVERSE EVENT AND SERIOUS ADVERSE EVENTS**

### **10.1        Definition of an Adverse Event (AE)**

An AE is any untoward medical occurrence in a clinical study subject, temporally associated with the use of a study product, including any acclimatisation, washout or lead-in product (or medical device), whether or not considered related to the study product, including any acclimatisation, washout or lead-in product (or medical device).

**NOTE:** An AE can therefore be any unfavorable and unintended sign (including an abnormal laboratory finding), symptom, or disease (new or exacerbated) temporally associated with the use of a study product including any acclimatisation, washout or lead-in product (or medical device).

Property of GSK Consumer Healthcare - Confidential

May not be used, divulged, published or otherwise disclosed without the consent of  
 GSKCH

CCI

Clinical Protocol Template v7.0

Page 64 of 100

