**Events NOT meeting the AE definition:**

- Any clinically significant abnormal laboratory findings (if applicable) or other abnormal safety assessments which are associated with the underlying disease, unless judged by the investigator to be more severe than expected for the subject's condition.
- The disease/disorder being studied or expected progression, signs, or symptoms of the disease/disorder being studied, unless more severe than expected for the subject's condition.
- Medical or surgical procedure (e.g. endoscopy, appendectomy) is not the AE. The condition that leads to the procedure is an AE (e.g. appendicitis).

Property of GSK Consumer Healthcare - Confidential

May not be used, divulged, published or otherwise disclosed without the consent of  
 GSKCH

CCI

Clinical Protocol Template v7.0

Page 65 of 100

- Situations where an untoward medical occurrence did not occur (social and/or convenience admission to a hospital).
- Anticipated day-to-day fluctuations of pre-existing disease(s) or condition(s) present or detected at the start of the study that do not worsen.

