4.5.2.2 OHT Examination

The OHT examination will be accomplished by direct observation, using retraction aids as appropriate and will identify any grossly carious lesions or signs of erosive wear, enamel irregularities, tooth fracture, gross decay, decalcification, and faulty restorations.

The presence of any implants, fixed or removable dentures, fixed or removable orthodontic braces/bands, fixed orthodontic retainers, full crowns or veneers will be recorded. Observations will be listed as either absent or present, and conditions noted as present will be described in

3% PVM/MA + 5% KNO₃ Toothpaste
218220

the eCRF. Any change observed by the clinical examiner or reported by the subject from the OHT examination carried out at Screening will be recorded as an AE.

OHT examination will be listed (Listing 16.2.8.2) for all randomized subjects.

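### The oral hard tissue rule makes any change from Screening an AE, in either direction, against the protocol's own AE definition; the effect is minor and a wording change fixes it.

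*Protocol*

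**What the plan says.** Protocol 9.3.2 describes the OHT examination. It looks for decay, fracture, erosive wear, faulty restorations and similar defects, and notes implants, dentures, braces, crowns and veneers. The scoring is binary: "Observations will be listed as either absent or present, and conditions noted as present will be described in the eCRF". The reporting rule, under which the entry is made as an AE, is: "Any change observed by the clinical examiner or reported by the subject from the OHT examination carried out at Screening will be recorded". SAP 4.5.2.2 carries the same rule with no added qualifier: "Any change observed by the clinical examiner or reported by the subject from the OHT examination carried out at Screening" is to be recorded as an AE.

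Three other places in the protocol bear on this:

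- **Section 9.3.1**, the oral soft tissue (OST) examination, uses a narrower trigger: "Any abnormality or worsening of a pre-existing condition observed by the clinical examiner" or reported by the subject.
- **Section 10.1** opens its definition with "An AE is any untoward medical occurrence in a clinical study subject", and its note describes an unfavourable and unintended sign, symptom or disease.
- **Section 10.1, events not meeting the definition**, says "Medical or surgical procedure (e.g. endoscopy, appendectomy) is not the AE"; the condition that led to the procedure is.

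Treatment emergent AEs are the sole safety endpoint (Protocol Table 3-1). Protocol 12.3.3 and SAP 4.5.1 count an AE as treatment emergent from first study product use at Baseline onward. SAP 4.5.1 tabulates TEAEs by oral/non-oral class (Table 14.3.1.2) and lists the oral ones separately (Listing 14.3.2.4).

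**The concern.** A change on an absent/present record can go either way. A faulty restoration that has been repaired moves from present to absent; a newly placed crown moves from absent to present. Under the OHT rule both are AEs. Under Section 10.1 neither is: the first is not untoward, and the second is a procedure whose cause is the event.

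Two kinds of entry could follow. One is an AE with nothing adverse behind it. The other is a second AE for a problem already recorded, such as a fracture and then the crown that treated it. OHT results are otherwise only listed, not tabulated (Protocol 12.3.3, SAP 4.5.2.2). AE recording is therefore the route by which an OHT change reaches a summary table.

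The protocol also gives the site two instructions that disagree, so staff could treat the same finding differently depending on which section they follow.

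**Working it through.** The documents give no figure for OHT changes, so there is no stated number to reproduce. The check is a comparison of rules, followed by an illustration of scale.

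**Step 1: apply each rule to the same finding.**

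| Finding at Week 8 against Screening | OHT rule (9.3.2; SAP 4.5.2.2) | Limit used for OST (9.3.1) | Section 10.1 |
|---|---|---|---|
| New tooth fracture | AE | AE | AE |
| Decay worse | AE | AE | AE |
| Faulty restoration repaired | AE | Not an AE | Not an AE: not untoward, and a procedure |
| Crown placed after a fracture | AE | Not triggered as a worsening | The fracture is the AE; the crown is not |

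The rules agree on harms. They part only on favourable changes and on dental work, where the OHT rule stands alone.

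**Step 2: look for a step that would remove such entries.** Under SAP 4.5.1, AEs are reviewed before database lock and unblinding, coded, and classed as oral or non-oral. Neither that section nor Protocol 12.3.3 provides for rejecting an entry that is not untoward.

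**Step 3: trace the path to the endpoint.** An entry recorded as an AE with onset on or after first product use is a TEAE. If classed as oral, it appears in Table 14.3.1.2 and Listing 14.3.2.4. An entry with onset before first use does not count as treatment emergent.

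**Step 4: scale.** With about 30 subjects per arm (Protocol 12.1), one subject with such an entry is 1/30 = 3.3 percentage points. To see how often this might arise, let p be the share of subjects with a favourable or neutral OHT change. The values of p below are assumptions, not figures from the documents. Expected entries are n × p, and the chance of at least one is 1 − (1 − p)^n.

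| Assumed p | Expected per arm (n = 30) | Chance of at least one in a given arm | Expected in trial (n = 120) | Chance of at least one in trial |
|---|---|---|---|---|
| 1% | 0.3 | 26% | 1.2 | 70% |
| 2% | 0.6 | 45% | 2.4 | 91% |
| 5% | 1.5 | 79% | 6.0 | 99.8% |

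Even a low rate would probably produce an entry or two somewhere in the trial if the rule were followed to the letter. The expected count per arm stays below one unless p exceeds 1/30 = 3.3%.

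**The case against.** The best defence is that Section 10 supplies the filter. Section 10.4 makes investigators responsible for events that meet the AE definition, and Section 10.1 deals directly with procedures. On this reading, 9.3.2 only tells the examiner to pass OHT changes on, and Section 10 decides what qualifies. A sensible site may well work that way. But 9.3.2 does not say that a change is to be assessed; it says that it will be recorded as an AE. That is specific and mandatory, so the two instructions conflict and neither qualifies the other.

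The second defence stands in large part: the situation is uncommon. Protocol 6.8 defers non-emergency dental treatment, Section 5.2 requires good oral health, and Section 5.3 excludes subjects who need extensive dental therapy. What remains is mostly emergency work, which normally has a genuine AE behind it. The usual error would then be double recording of a real event.

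A reader might go further and infer that a change first seen at Week 8 would be dated as on-treatment. The inference is tempting because OHT is done only at Screening and Week 8, and at nominal visit times the run-in is 14/(14 + 56) = 20% to 28/(28 + 56) = 33% of that interval. The documents do not support it. SAP 4.5.1 classifies by onset date and time and does not make the date of detection the onset. Run-in events are also sought by other routes: AEs are collected from consent (10.3), subjects are asked about them at Baseline (8.2.1), and the diary covers oral problems from Screening (6.7). Section 10.1 also accepts that a condition detected after product use may have been present earlier.

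A reader might likewise infer that comparisons between arms would be distorted. No between-arm safety test or decision rule is planned, the examiner is blinded, and AEs are reviewed before unblinding. Nothing in the documents points to one arm gaining more of these entries than another.

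**Conclusion.** The rule is wrong as written, and the matter is minor. Protocol 9.3.2 and SAP 4.5.2.2 require an AE for any OHT change in either direction. This contradicts the AE definition and the procedure exclusion in Section 10.1, and departs from the OST rule in 9.3.1 without a stated reason. Followed literally, it can put entries that are not untoward into the oral TEAE table.

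Their number cannot be derived from the documents and is probably small. The 3.3 percentage points describes one hypothetical subject in an arm of 30, and the probabilities above rest on assumed rates and on literal compliance. The conclusion covers AE recording and the tables built on it. It does not touch the performance analyses, and it does not extend to wrongly dated Week 8 findings or to bias between arms.

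**What to change.** In Protocol 9.3.2 and SAP 4.5.2.2, replace the open-ended trigger with: *Any new abnormality, or worsening of a pre-existing condition, relative to the Screening OHT examination.* Then state that other changes (repairs, new restorations or prostheses) are listed as OHT findings or treatments, and that the condition which led to them is assessed as the AE under Section 10.1.

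The word *new* matters. The OST sentence begins "Any abnormality or worsening of a pre-existing condition observed by the clinical examiner or reported by the subject from the OST examination". Copied as it stands, it could be read to make an abnormality already present at Screening an AE. Erosive wear is an OHT item, and every subject must have exposed dentine from erosion, abrasion or recession (Protocol 5.2), so that reading could create the very entries the change is meant to prevent.

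Optionally, Listing 16.2.7.1 could flag OHT-derived AEs first seen at Week 8 with unknown onset. Flagged events would stay in the TEAE tables.

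The cost is a sentence or two in each document. No examination, data item or analysis is added, and genuine hard tissue harms are still captured. Because the protocol text changes, the edit is best carried with other amendments.
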